The current project proposes to examine the feasibility, acceptability, and potential effectiveness of our novel response-adaptive app intervention, Mobile After-Care Support (MACS), to improve treatment adherence and self-coping in psychosis following hospitalization, in preparation for a future full-scale clinical trial. We propose to enroll hospitalized patients with schizophrenia spectrum disorders prior to discharge and provide them with the MACS app to use during the first 4 months post-discharge to improve adherence to oral psychotropic medications, appointment attendance, and active self-coping with illness. We will conduct a pilot randomized controlled trial (RCT) of MACS to assess its impact on outcomes of interest relative to an attention-matched control condition. We also will conduct qualitative interviews with clinician stakeholders.

Aim 1: Conduct a pilot RCT (n = 80) of MACS vs mobile app attention control. We will assess: a) acceptability/satisfaction with the mobile app; b) feasibility of the RCT design (e.g., recruitment, randomization, assessments); c) whether the mobile app improves our proposed target mechanisms of increased illness self-coping and treatment adherence; d) whether our mobile app improves primary (symptom severity) and secondary (functioning, rehospitalization) outcomes; and e) whether changes in our adherence and coping target mechanisms predict changes in clinical outcomes.

Aim 2: Conduct 30-minute, individual qualitative interviews with 20 clinical stakeholders (including support staff, clinicians, and administrators) at mental health hospital and outpatient treatment centers in the

RI area. Stakeholder interview agendas will assess: a) perceived barriers to patients' medication/appointment adherence, b) use of mobile devices to support aftercare, c) potential self-management strategies to improve patients' coping, d) challenges patients face upon return to the community post-discharge, e) challenges faced by clinicians/organizations treating this population, and f) preferences regarding the flow of information collected via EMA and what data would be most useful.

B. Background

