To maintain stability in patients with schizophrenia requires effective self-management of symptoms and consistent treatment adherence. Perhaps the most notable period in the continuum of care when coping and medication/appointment adherence are jeopardized is during the first months following discharge from acute hospitalization. Various factors associated with adherence have been described in our pilot work, and we have used these data to inform the development of a theoretically- and empirically-grounded, mobile intervention app following hospitalization, which we are currently in the process of developing. We will test the feasibility, acceptability, and potential effectiveness of our mobile app, that we call Mobile After-Care Support (MACS), to improve the target mechanisms of active illness self-coping and medication/appointment adherence post-hospital discharge. We plan to compare the MACS app to an attention-matched app that will assess variables of interest and provide non-adaptive information (i.e., education) in the context of a RCT design for patients recently hospitalized for psychosis. To aid in app development and planning, we will also conduct qualitative interviews of clinical stakeholders regarding their perspectives on the app.

C. Experimental Method

C1. Brief Description of Subjects

Study A. Participants in this study will consist of 80 patients diagnosed with schizophrenia-spectrum disorders who have been hospitalized for acute psychiatric reasons at Butler Hospital. See detailed inclusion/exclusion criteria below.

Study B. We also will select 20 clinical stakeholders for participation. These participants will be selected from clinicians, administrators, and support staff working at Butler Hospital, The Providence Center, and other mental health programs in the area. We do not propose recruiting a specific number of each group at this point. As is typical of qualitative methods, we will interview stakeholders until we have reached saturation on relevant themes. Therefore, the numbers for each type of stakeholder recruited will vary; although we will attempt to interview several for each category. See detailed inclusion/exclusion criteria below.

C2. Study Design

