Study A. We will use the pilot RCT ($n = 80$) to assess MACS acceptability/ feasibility and its preliminary effectiveness relative to a control condition. Randomization will be used to help ensure balance among treatment conditions. We will stratify by diagnosis (schizophrenia/schizopreniform vs schizoaffective) and by gender (male vs female). We will conduct randomization using a computer generated list via REDCap held by a staff person no otherwise affiliated with the study. We will review patient acceptability/ satisfaction ratings and ease of use of mobile devices as measured by the CSQ-8 and patient qualitative interviews. These data will inform further refinements of the MACS app that will be used in future research.

Study B. We also will conduct 30-minute individual interviews of clinical stakeholders ($n = 20$). Interviews will be led by members of the investigator team and a study research assistant (RA) listening to the conversation and taking notes. Interview agendas will be developed so that participants will receive similar types of questions, as well as those that may be specific to their job responsibilities (e.g., clinician vs administrator).

C3. Specific Procedures or Treatments

MACS Protocol. We will use an established mobile software service (ilumivu.com) which provides a secure platform (Android or Apple IOS compatible) that can be programmed to administer the MACS app. It does not require a high degree of IT support and allows for tailoring of content without the need for trained programmers. Further, we chose a mobile app that works with most smartphones, is easy to download/install, and runs largely autonomously. Because we are using a flexible software platform to deliver our mobile intervention and not a static app specifically designed for this project, we have flexibility to make changes to the content of the app during the project in an iterative fashion based on what we learn from the data being collected. In addition, future implementation of the app can take advantages of ongoing improvements and updates to the platform that will be used in future iterations of our app-based interventions that would be proposed for a next step full-scale RCT if this project is successful.

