Mobile Software Service. We will use an established mobile software service (ilumivu.com) which provides a secure, HIPAA-compliant application (Android or Apple IOS compatible) that can be programmed to administer the MACS app and the attention control app. Responses will be uploaded when internet/cellular access is available to a web portal for remote access/downloading from a convenient web portal interface. Otherwise, responses are stored on the native app in an encrypted format until uploading can occur. App updates and fixes can also be sent remotely to the app when needed. Raw app data will not be automatically sent to providers. Instead, staff will review mobile data weekly to monitor safety and contact patients if safety risk is detected. Patients will be informed that mobile data will not be reviewed in real time and that they should contact providers/seek immediate help if needed. These risk data will also be included in the periodic reports that are sent to providers. Patients will be prompted by the device to contact a crisis hotline, their providers (numbers pre-programmed into the device), or 911/local hospital if they report an immediate safety risk.

Mobile Device Training/Support. For individuals in both conditions, after obtaining consent at hospitalization (baseline), a research assistant will help patients install the app on their own smartphone when possible for convenience. If a patient is unwilling to install the app or does not own a compatible smartphone, we will supply a dedicated mobile device to the participant for this purpose post-discharge and they will return the device at the end of the study. Patients will practice responding to app sessions to familiarize themselves with the program and troubleshoot technical problems. Patients will be instructed to contact the study if questions arise post-discharge about using the device. For individuals in the MACS condition only, we also will employ a master's level clinician to meet with participants to review their discharge plan prior to leaving the hospital and discuss how to use the app to support their aftercare. For both conditions, app training/support meetings will be held prior to discharge when possible. If a patient is unexpectedly discharged, participants will be asked to return to our clinic, and this meeting will be held as shortly after discharge as possible, or it will be conducted over the phone if the participant is unable to return to the clinic.

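### Aim 1(c)-(d) asks about the mobile app, but the randomized contrast estimates a MACS package of app, clinician discharge-plan meeting and provider reports

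*Combined protocol and SAP*

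**What the plan says.** **The question.** Aim 1(c) asks "whether the mobile app improves our proposed target mechanisms" and Aim 1(d) asks "whether our mobile app improves primary (symptom severity) and secondary (functioning, rehospitalization) outcomes". The Specific Aims give the purpose of the trial as "to assess its impact on outcomes of interest relative to an attention-matched control condition". The Background puts it more narrowly: "We plan to compare the MACS app to an attention-matched app".

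**What both arms get.** C3 gives both apps the same prompt frequency and the same assessment items. Both arms get a research assistant's help with installation, practice sessions and an app training/support meeting. Weekly safety review of app data, and clinician evaluation when risk is found, are not limited to either arm (C3, Mobile Software Service; D1; D3).

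**What only the MACS arm gets.** Apart from the adaptive content, there are two elements.
- C3, Mobile Device Training/Support: "For individuals in the MACS condition only, we also will employ a master's level clinician to meet with participants to review their discharge plan". The clinician also discusses how to use the app in aftercare.
- C3, MACS communication with outpatient providers: an initial discharge report and then periodic reports, once releases are obtained. Section 3.B repeats that the reports are for patients randomized to MACS.

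Section E assigns both tasks to the same clinician.

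**The analysis.** C2 refers to MACS and "its preliminary effectiveness relative to a control condition". C4 models treatment condition, time and their interaction. Its caveat concerns wide confidence intervals, not attribution.

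**The concern.** If Aim 1(c)-(d) is answered as written, a favourable between-arm difference becomes a statement about the app, although it could come partly from the meeting or the reports. The protocol itself expects the reports to do something. C3, MACS Protocol, says information on logistical reasons for nonadherence goes to providers so that the clinic can contact the patient, and the communication section gives better care coordination as the purpose. Adherence is among the target mechanisms. A patient who answers the surveys but makes little use of the adaptive exercises could still benefit through the clinic or the discharge-plan review.

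At stake is what the pilot may conclude and what it passes on. C4 expects some pilot parameters to help in planning a full-scale trial. A later trial of the app alone would be relying on results from a different intervention.

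**Working it through.** The plan gives no figure to reproduce on this point: no power, effect size or standard deviation lies behind the 80. The check is a comparison of the arms, followed by the question of what one contrast can identify.

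**Step 1. Components by arm.**

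| Component | MACS | Control | Source |
|---|---|---|---|
| Assessment items, prompt frequency | yes | same | C3, Attention Control Protocol; Assessments |
| Installation help, app training | yes | yes | C3, Mobile Device Training/Support |
| Safety review and contact | yes | yes, not limited by arm | C3, Mobile Software Service; D1; D3 |
| Content after the survey | adaptive, interactive | fixed didactic text | C3, both app protocols |
| Clinician discharge-plan review | yes | no | C3, Mobile Device Training/Support |
| Initial and periodic provider reports | yes, with releases | no | C3, MACS communication; 3.B |

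The last three rows differ.

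**Step 2. What the contrast estimates.** Let A be the effect of adaptive over didactic content, M the effect of the meeting, R the effect of the reports, and I any interactions. The between-arm difference is D = A + M + R + I. The trial yields one contrast for four unknowns. A sample larger than 80 would narrow the interval around D but would not separate A from M + R + I.

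**Step 3. Are the reports simply part of the app?** The periodic reports use app data, but both apps ask the same items. The initial report uses assessment results, and both arms have baseline assessments. The raw material therefore exists in both arms; the control arm goes without reports by design. R is distinct from the adaptive content.

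**Step 4. Could MACS patients without a release serve as an app-only group?** No. They would receive no reports but are still due the meeting, and they are self-selected.

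**Step 5. Number of reports, for illustration only.** The schedule in C3 is given as an example, and bi-weekly can be read two ways.
- Every two weeks in month 1, then monthly in months 2-4: 1 + 2 + 3 = 6, or 1 + 2 + 2 = 5 with none at the end of month 4.
- Twice a week in month 1 (four weeks), then monthly: 1 + 8 + 3 = 12.
- One at each of the 1-, 2- and 4-month follow-ups, a possible reading of 3.B: 1 + 3 = 4.

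So the count is 4 to 12 on these readings, against 0 in control. The conclusion does not depend on which applies.

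**Step 6. The meeting.** Section E describes the clinician as meeting patients for the initial app session, so this may be the same session as the app training that both arms receive. The difference in content is documented; a difference in the number of contacts is not. Under the Remote Recruitment Procedures (3.B), inpatients consent by phone after discharge, so for them the meeting cannot precede discharge. C3 allows a later or telephone meeting after an unexpected discharge, but the remote text mentions only app orientation. The provider reports remain a difference either way.

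**The case against.** The best defence is that this is shorthand and hides nothing. The Aim 1 stem, C2 and C4 compare MACS or treatment condition with control, and C4 credits nothing to the app alone. The extra elements are openly described: the reports appear within the MACS Protocol text and under their own heading. Testing a package in a two-arm pilot is legitimate. C4 puts feasibility and acceptability first and warns that the effect analyses may not be conclusive. Its example of a parameter to carry forward, the stability of outcome measures over time, does not depend on attribution.

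Most of this stands, and it limits the impact. It does not remove the mismatch. Usage of MACS is mixed: C3 also refers to a MACS condition and a MACS intervention, but the Specific Aims speak of "our novel response-adaptive app intervention, Mobile After-Care Support (MACS" (the quotation stops before the closing bracket), and the Background of the "potential effectiveness of our mobile app, that we call Mobile After-Care Support (MACS" in the same way. The word alone therefore does not tell a reader that the package is meant, and no passage limits attribution.

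A reader might infer more than the documents support in three ways:
- That control patients have no clinician contact. Training meetings and safety-related contact are not confined to MACS.
- That the number of contacts or reports measures the bias. The counts rest on ambiguous wording and are not effect sizes.
- That the reports are shown to act on both medication and appointment adherence. The MACS Protocol ties clinic outreach to logistical reasons for nonadherence; for missed appointments it names only problem-solving strategies. The wider reading is an inference from the general adherence content of the reports.

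**Conclusion.** The concern holds as a mismatch between the question asked and the effect estimated. The randomized comparison is valid for the MACS package; an app-only answer to Aim 1(c)-(d) is not available from this design at any sample size. A reader might go further and conclude that the trial is biased or that the analysis plan makes an app-only claim. The documents support neither.

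The practical impact is modest, because this is a pilot with preliminary effect analyses. The share of any difference due to the meeting or the reports cannot be calculated from the documents. The conclusion assumes only that the two MACS-only elements are delivered to at least some patients as C3 describes. If the meeting is often displaced under the remote procedures, the reports alone sustain the point.

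**What to change.** 1. **Specific Aims, Aim 1(c)-(d).** Replace *the mobile app* and *our mobile app* with *the MACS intervention (adaptive app, clinician discharge-plan meeting and provider reports)*. Keep the parenthesis, because MACS is elsewhere introduced as the app.
2. **Specific Aims and Background.** State that the control is matched on prompt frequency, assessment items, app installation help and app training, but not on the MACS-only discharge-plan meeting or the provider reports. Do not write that it is unmatched on clinician contact in general, since safety-related contact is not limited to either arm. The name attention control can stay.
3. **C4.** Add: *Between-arm differences estimate the effect of the MACS package; no effect will be attributed to the app alone.*

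Optionally, record and report descriptively whether the clinician meeting took place and how (in person or by phone, including under the remote procedures), which releases were signed and which reports were sent. This would show what was delivered; it would not separate the components.

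The cost is a few lines of text, plus a short log if wanted, and a narrower claim. Randomization, endpoints, sample size and visits stay as they are.

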Target Mechanisms. Our target mechanisms are increases in: a) medication adherence, b) appointment adherence, and c) active self-coping with illness. a) We will employ MEMS⁴⁵ to objectively measure medication adherence during the post-hospital period for the primary oral psychotropic medication prescribed for participants in both conditions based on the following hierarchy/order: 1) antipsychotic, 2) mood stabilizer, 3) antidepressant, or 4) anxiolytic/hypnotic. MEMS uses an electronic pill cap that records bottle openings/closings and the corresponding time/date^{46,47}. Patients will be trained by research staff to use MEMS at the start of the study. MEMS data will be downloaded at our research office at follow-up assessments and when patients receive medication refills. MEMS data will not be integrated into the MACS intervention and will be used instead for research data collection only. Similarly, pill counts also will be conducted at this time for back-up purposes. Electronic monitoring is recommended for objective adherence assessment⁴⁸; MEMS has been used in studies of schizophrenia⁴⁹, including in our R21 pilot study. b) For appointment adherence, we will use the THI-4⁵⁰, which is a treatment utilization interview, to assess mental health appointments missed/scheduled. Medication/appointment adherence will be cross validated by obtaining releases for patients' outpatient medical records, and any discrepancies will be re-reviewed with the patient to obtain an accurate count. c) Coping with illness in schizophrenia will be assessed via the standardized and well-validated MACS-II^{51,52}. MACS-II is an interview-based measure that assesses coping to 13 core symptoms of schizophrenia, including positive and negative psychotic symptoms, depression, cognition, hostility, and euphoria. Coping responses are then categorized based on 5 coping styles described by Carr⁵³, including passive illness behavior (e.g., lying in bed and doing nothing), active problem-solving (e.g., professional help seeking), passive problem-avoiding (e.g., isolation), active problem-avoiding (e.g., indulgence), and symptomatic behavior (e.g., obeying voices). Research has shown the MACS-II to be reliable and valid when used in samples with schizophrenia⁵⁴. We also will administer the following: the BARS⁵⁹ which is a interview assessing the patient-reported percentage of missed doses over the past month for the primary oral psychotropic medication; the SUS⁶⁰ which is a 10 item self-report of app usability; the USE⁶¹ which is a 30 item self-report of app satisfaction; the Brief COPE⁶² which is a 28 item self-report measure of coping skills; and the PUQ which is a self-report measure we created for this study to collect data on participants' use of mobile phones and related technology.

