
Table 1. Traditional Assessments

	Construct assessed	Method	Time
Structured Clinical Interview for DSM-5 (SCID-5; Psychotic, Mood, Substance Use Modules) ⁵⁵	Axis I diagnosis	Interview	Baseline (BL)
Mini-Mental State Exam (MMSE) ⁶³	Cognitive functioning	Interview	BL
Phone Usage Questionnaire (PUQ)	Phone use	Self-Report	BL
Medication Event Monitoring System (MEMS) ⁴⁵	Medication adherence	Objective	1,2,4
Antipsychotic Medication Beliefs and Attitudes Scale (AMBAS) ⁶⁵	Medication beliefs	Self-report	BL,1,2,4
Brief Adherence Rating Scale (BARS) ⁵⁹	Medication adherence	Interview	BL,1,2,4
Treatment History Interview-4 (THI-4) ⁵⁰	Appointment adherence	Interview	BL,1,2,4
Outpatient chart/medical records review	Treatment utilization	Objective	BL,1,2,4
Maastricht Assessment of Coping Strategies (MACS-II) ^{51,52}	Coping skills	Interview	BL,1,2,4
Brief Coping Orientation to Problems Experienced (COPE) ⁶²	Coping skills	Self-Report	BL,1,2,4
Brief Psychiatric Rating Scale (BPRS) ⁵⁶	Psychiatric symptoms	Interview	BL,1,2,4
WHO Disability Assessment Sched. 2.0 (WHODAS-2) ⁴⁰	Functioning	Self-Report	BL,1,2,4
Alcohol Use Disorders Identification Test (AUDIT) ⁴²	Alcohol use	Self-Report	BL,1,2,4
Drug Use Disorder Identification Test (DUDIT) ⁶⁴	Drug use	Interview	BL,1,2,4
Usefulness, Satisfaction, and Ease of Use Questionnaire (USE) ⁶¹	Acceptability	Self-Report	1,4
System Usability Scale (SUS) ⁶⁰	Acceptability	Self-Report	1,4
Client Satisfaction Quest.-8 (CSQ-8) ⁵⁷	Acceptability	Self-report	1,4

Date most recently revised 6/14/2021

Protocol Version 1.9

End of Treatment Interview	Feedback	Interview	1,4
----------------------------	----------	-----------	-----

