We will use effect size changes to describe differences between groups over the time points on target mechanisms (adherence and coping), primary outcomes (overall symptom severity), and secondary outcomes (functioning, rehospitalization rates). We will calculate 95% confidence intervals (CIs) and clinical significance statistics (e.g., NNT). Because CIs will likely be large, these analyses may not permit definitive conclusions. Given the limitations and goals of pilot studies, we hope to build our case for future research by focusing primarily on the feasibility/acceptability of MACS and of the randomized design and the clinical significance of effects compared to our mobile attention control. Some parameters estimated in the pilot study (e.g., stability of outcome measures across time) may be helpful for informing estimates for a large scale, adequately powered RCT. Secondarily and consistent with analyses we would conduct in a future full-scale RCT, we will generate multilevel models to examine whether treatment condition, time, and the treatment condition X time interaction predicts change in outcomes (symptoms, functioning, re-hospitalization) and proposed mechanisms. Generalized estimating equations will be constructed to examine differences in rehospitalization rates over time. We will assess whether the groups differ on covariates at baseline (e.g., demographics) and, if so, include them in the statistical models. Given the smaller sample size, we will examine changes in mediators over time across conditions and correlations between mediators and outcomes, which are pre-requisites for formal mediation. We also will examine outcome predictors (e.g., baseline adherence) to identify possible moderators to test in future studies

Qualitative interviews will be recorded and the interviewer will keep notes of the conversation. The MPIs will develop an initial codebook with deductive codes. Then inductive codes capturing emergent themes will arise from team-level review of interviews. Once codes are developed, the research team will independently code remaining transcripts; 20% of transcripts will be double coded and reviewed to ensure inter-rater reliability. The MPIs will perform thematic analysis in which the passages assigned to codes will be read in aggregate to identify key themes.

C5. Videoconferencing

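### MEMS has no pre-intervention value, so C4 should name the between-arm difference in MEMS level, over a stated window, as the MEMS effect

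*Combined protocol and SAP*

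**What the plan says.** **Schedule.** In Table 1 (Traditional Assessments) the row "Medication Event Monitoring System (MEMS" carries times 1, 2 and 4, with no baseline. The row "Brief Adherence Rating Scale (BARS" carries baseline, 1, 2 and 4. So do THI-4, MACS-II, Brief COPE, BPRS and WHODAS-2.

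**What is measured.** C3 (Target Mechanisms) uses MEMS "to objectively measure medication adherence during the post-hospital period for the primary oral psychotropic medication". BARS is an "interview assessing the patient-reported percentage of missed doses over the past month for the primary oral psychotropic medication". Under A. Specific Aims, the app is used for the first four months after discharge, so the month 1 MEMS value is already an on-treatment value.

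**Analysis.** C4 begins: "We will use effect size changes to describe differences between groups over the time points on target mechanisms (adherence and coping", followed by the primary and secondary outcomes. Secondarily, multilevel models examine whether "treatment condition, time, and the treatment condition X time interaction predicts change in outcomes (symptoms, functioning, re-hospitalization) and proposed mechanisms". For mediation, the plan is to "examine changes in mediators over time across conditions and correlations between mediators and outcomes". The covariate rule is: "We will assess whether the groups differ on covariates at baseline (e.g., demographics) and, if so, include them in the statistical models". C4 makes no exception for MEMS, does not name the term or contrast that is the treatment effect, and does not give the coding of time. It calls the models consistent with those intended for a full-scale trial.

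**The concern.** For a measure with a baseline taken before the intervention, condition × time can carry the treatment effect, because the arms start level in expectation and separate afterwards. MEMS lacks that starting point. If it is read in the same way as BPRS or BARS, any benefit already present at month 1 drops out of the interaction and out of month 1–4 change.

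Such a pattern is plausible here. C3 (Mobile Device Use) has three prompts a day in month 1 and one a day in months 2–4, so an early effect that holds or fades is a natural possibility. MEMS is the objective measure of the first-listed target mechanism. A false null or a reversed sign could misinform the later trial that this pilot is meant to prepare.

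**Working it through.** **Inputs.** From the documents: MEMS visits at months 1, 2 and 4, and 80 participants randomised. The documents give no SD, correlation, effect size, alpha, power or allocation ratio, and no derivation of the 80, so there is no stated figure to reproduce. The following are assumptions: 40 per arm, MEMS SD 30 percentage points, the same within-person correlation of 0.6 between any two visits, two-sided 5% tests, and the gain profiles below.

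**What each term estimates.** Let d1, d2 and d4 be the true MACS-minus-control differences at the three visits. The mean visit time is 7/3 months.

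- Level (equal weights): (d1 + d2 + d4)/3
- Month 1–4 change: d4 − d1
- Linear condition × time: (−4·d1 − d2 + 5·d4)/14 per month
- Condition term with time origin t0: level + slope × (t0 − 7/3)

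The weights of the change and of the slope each sum to zero, so any constant difference gives exactly 0. This is algebra and needs no assumption about SD or correlation.

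| Profile d1/d2/d4 | Level | Change | Interaction per month | Condition term, origin month 0 | month 1 | month 4 |
|---|---|---|---|---|---|---|
| Sustained 15/15/15 | 15 | 0 | 0 | 15 | 15 | 15 |
| Waning 22/18/12 | 17.3 | −10 | (−88 − 18 + 60)/14 = −3.3 | 25.0 | 21.7 | 11.9 |
| Growing 8/15/22 | 15 | +14 | (−32 − 15 + 110)/14 = +4.5 | 4.5 | 9.0 | 22.5 |

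With time centred, the condition term equals the level. In the waning case the month-0 term (25.0) exceeds the largest true difference at any visit (22), because month 0 lies outside the range of the three visit values.

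**Illustrative precision.**

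- SE of level = √[2·900·(1 + 2·0.6)/(3·40)] = √33 = 5.74, so the 95% CI is ±11.3.
- SE of slope = √[2·900·(1 − 0.6)/(40·14/3)] = √3.86 = 1.96.
- Sustained: level detected 74% of the time, interaction 5% (the alpha).
- Waning: level 85%; interaction significant, in the negative direction, about 39%.
- Growing: level 74%, interaction 63%.

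For the sustained profile, level power is 78% to 71% at correlations of 0.5 to 0.7, and 65% with 32 per arm. It runs from 32% (SD 35, gain 10) to over 99% (SD 20, gain 20). Interaction detection stays at 5% in all of these.

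**The window matters too.** If each visit value summarises the interval since the previous one, the windows last 1, 1 and 2 months. Weighting by time gives (22 + 18 + 2·12)/4 = 16.0 instead of 17.3 for the waning profile, and (8 + 15 + 2·22)/4 = 16.75 instead of 15 for the growing one. A level contrast therefore needs its window and weights stated.

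**Adjustment for baseline BARS.** If baseline BARS correlates r with MEMS at each visit, the SE of level is √[45·(0.7333 − r²)]: 5.59 at r = 0.2 and 4.66 at r = 0.5. The true r is unknown.

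**The case against.** - **MEMS is a continuous record.** C3 says that the cap logs the date and time of openings, that training takes place when the study starts, and that data are downloaded at follow-ups and refills. A reader might infer that MEMS can show nothing before month 1. The documents do not support that: daily or weekly bins would show movement within month 1, and recording starts near month 0. This stands, so the zero and negative results hold only for a three-visit summary. Finer bins still give no pre-intervention value.
- **C4 never says that the interaction is the effect.** It lists condition as its own term and describes group differences at the visits with 95% CIs. A reader might infer that C4 offers no valid MEMS analysis. That is not so: randomisation makes a post-baseline comparison of levels valid. What remains is that this contrast is not named, and that with linear time the condition term changes with an unstated origin. Time coding is unstated for every outcome; only MEMS also lacks a baseline.
- **BARS and THI-4 have baselines.** Neither Aim 1(e), which asks about change in the mechanisms, nor the baseline-adherence predictor in C4 names MEMS. These analyses remain possible. BARS is patient-reported, however, and does not prevent a misreading of the objective measure.
- **Baseline BARS may predict poorly.** It covers a month that includes or adjoins a hospital stay. This is fair: the gain in precision is uncertain.
- **The covariate rule and the strata affect every model.** True. They are raised here only because they bear on how the MEMS contrast is adjusted, and they add no weight to the finding.

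**Conclusion.** The point holds in a limited form. MEMS has no pre-intervention value, and C4 applies wording about change and condition × time to all mechanisms without an exception. With MEMS summarised at months 1, 2 and 4, a benefit reached by month 1 and held gives zero on those measures, and a waning but persistent benefit gives a negative coefficient. That follows from the schedule alone. The sizes (−3.3 points per month, the condition terms, the power figures) rest on assumed profiles, SD and correlation, and are illustrative only.

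The consequence is modest. It concerns one measure of one mechanism, in models that C4 calls secondary, in a pilot for which C4 itself doubts definitive conclusions. BPRS has a baseline and is unaffected. The change is still worth making, because C4 presents these models as the pattern for the full-scale trial.

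**What to change.** In C4:

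1. Define the MEMS effect as the between-arm difference in level, and state the window that each value covers. Examples are percent of prescribed doses taken from MEMS start to month 4, or interval-specific values with stated weights. Use categorical time and give interval-specific estimates with 95% CIs.
2. Adjust for baseline BARS and the gender stratum whether or not the arms look unbalanced. Add the diagnosis stratum once two sections are reconciled: C2 stratifies schizophrenia/schizophreniform against schizoaffective, while Subject Population (section 3A) also admits mood disorder with psychotic features.
3. Treat MEMS condition × time only as a test of whether the effect changes over follow-up.
4. Use BARS wherever change from baseline in medication adherence is needed.

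The cost is three or four sentences and no new data, since baseline BARS and gender are already collected. The diagnosis adjustment also needs a statement of how participants with mood disorder are classified at randomisation.
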